6.11.2. Other Secondary Safety Analyses

The analyses described in Section 6.11.2 will include data collected for the Safety Population including data collected prior to permanent discontinuation (i.e., last dose) of IP in each 6-week treatment period. In addition, other than severe hypoglycemia events, all secondary safety endpoints are pump-related, and therefore the corresponding analyses will also exclude data (if any) that are collected while patients temporarily are off pump or off IP.

For the following secondary safety endpoints, the incidence (percent of patients with at least 1 event) and rate will be analyzed using Prescott's exact test and Wilcoxon signed-rank test, respectively, as described above for the primary endpoint.

- suspected infusion set occlusions defined as unexplained hyperglycemia with blood glucose (SMBG) >250 mg/dL (13.9 mmol/L) that does not decrease within 1 hour (+10 minutes) following a correction bolus delivered via the pump and that leads to an infusion set change
- infusion set failures leading to premature infusion set changes due to unexplained hyperglycemia with blood glucose >250 mg/dL that does not decrease by >50 mg/dL within 1 hour (+10 minutes) following a correction bolus delivered via the pump
- premature infusion set changes for any reason and for each individual reason (infusion set kinked, came out or leaking; empty pump reservoir; infusion site pain or redness; pump occlusion alarm; suspected infusion set occlusion; other)
- severe hypoglycemic events

For the infusion set failures and premature infusion set changes, the number of events and the number of patients with events will be derived for each treatment group by infusion set catheter dwell time (≤ 24 hours, >24 and ≤ 48 hours, >48 and ≤ 72 hour, >72 hours), and overall (across over the course of approximately 72-hours of continuous infusion).

A listing of premature infusion set changes due to unexplained hyperglycemia will be generated. For each premature infusion set change due to unexplained hyperglycemia, the following information will be provided:

- whether it is an infusion set failure that meets the primary endpoint definition
- whether it is an infusion set failure that meets the secondary endpoint definition (i.e. leads to premature infusion set changes, due to a pump occlusion alarm OR due to unexplained hyperglycemia with blood glucose [SMBG] >250 mg/dL [13.9 mmol/L] that does not decrease by >50 mg/dL within 1 hour [+10 minutes] following a correction bolus delivered via the pump)
- the most recent SMBG within 1 hour before the correction bolus
- the 3 most recent CGM values within 20 minutes before the correction bolus
- the most recent SMBG within 1 hour (+10 minutes) following the correction bolus that was collected prior to the infusion set change
- the most recent SMBG within 2 hours (+10 minutes) following the correction bolus that was collected prior to the infusion set change
- the 3 CGM measures within the time interval of [1 hour-10 minutes, 1 hour+10 minutes] following the correction bolus that were collected prior to the infusion set change
- the 3 CGM measures within the time interval of [2 hour-10 minutes, 2 hour+10 minutes] following the correction bolus that were collected prior to the infusion set change
- the highest ketone testing value within ± 2 hours of the correction bolus
- the highest ketone test value within ± 2 hours of the infusion set change

Similarly, a listing of premature infusion set changes due to pump alarms and a listing of all premature infusion set changes will also be provided. The SMBG values, CGM values, and ketone test values relative to the infusion set change time will be provided. Both date and time

of all infusion set changes will be collected in the database by either eCRF or eCOA (Table ITSI.6.4).

Table ITSI.6.4. Source Data for Infusion Set Changes

Study Period	Infusion Set Changes	Data Source
Lead-in period	First infusion set change	eCRF: First Dose Open Label Lead-in Treatment
	Other infusion set changes- outside of the office visit	eCOA
	Last infusion set change	eCRF: Last Dose Open Label Lead-in Treatment ^a
Period I	First infusion set change	eCRF: First Dose Study Treatment Period I
	Other infusion set changes – outside of the office visit	eCOA
	Last infusion set change	eCRF: Last Dose Study Treatment Period I ^a
Period II	First infusion set change	eCRF: First Dose Study Treatment Period II
	Other infusion set changes – outside of the office visit	eCOA
	Last infusion set change	eCRF: Last Dose Study Treatment Period II ^a
Safety Follow-up	NA	NA

^a In extremely rare cases where patients stopped treatment on pump but continued to use treatment through syringe until they discontinue from the study, the last dose form will capture the timing of the last dose of treatment in CRF, which will not be the last infusion set change.

The last infusion set change in each treatment period (lead-in, Period I or Period II) occurs only when a patient comes to an office visit or early discontinuation of study treatment. This change is not reflective of patients' behavior regarding infusion set changes, and thus it will not be included in the derivation of time until infusion set changes. Patient-reported premature infusion set changes due to the reason "Other" or patient-reported routine infusion set changes that occur within 1 hour of a previous infusion set change (captured in the case report form [CRF]), will be treated as a redundant entry in eCOA and excluded from all analyses. In addition, any patient-reported routine infusion set change that occurred within 24 hours of a previous infusion set change could have been misreported as routine or are redundant entries in eCOA, and thus will be excluded from all analyses.

Time interval until infusion set change for each infusion set can be derived through a minute-to-day conversion by dividing the time difference between the infusion set change and its previous infusion set change by 1440 minutes. The protocol requires that patients change infusion set every 72 ± 4 hours unless a change is required for failure of the infusion set. To handle potential missing input in eCOA for the infusion set change, time interval until infusion set change greater than 7 days (168 hours) will be excluded. For each treatment period, time interval until infusion set change will be derived by averaging all infusion set changes within the period. The analyses will be conducted by an MMRM model (Model 2) as specified in Section 6.1.

Derivation and analysis of interstitial glucose reduction rate are described in Section 6.12.

Actual and change from baseline in total, basal, and bolus insulin doses and bolus/total insulin dose ratios will be compared between LY900014 and insulin lispro using an MMRM model (Model 1) as specified in Section 6.1. The doses and bolus/total insulin dose ratios for each visit will be calculated as the mean of the doses for the last 3 days prior to the visit. A listing of insulin doses will also be provided, including data collected at Visit 801.

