#### 10.3.3.2. Secondary Analyses

The incidence (percent of patients with at least 1 event) of infusion set failures, as defined in the primary objective, premature infusion set changes by reason, and severe hypoglycemia will be analyzed using Prescott's exact test.

Similarly, Wilcoxon signed-rank test will be used to analyze the rate of infusion set failures, premature infusion set changes by reason, and severe hypoglycemia, as described in Section [10.3.3.1](#).

As an additional analysis, the rate and incidence will be determined for infusion set failures leading to premature infusion set changes due to unexplained hyperglycemia with blood glucose >250 mg/dL that does not decrease by >50mg/dL within 1 hour following a correction bolus delivered via the pump and analyzed in the same way as described for the primary endpoint.

For infusion set failures defined in the primary objective and premature infusion set changes, the number of events and the number of patients with events will be derived for each treatment group by infusion set catheter dwell time ( $\leq 24$  hours,  $>24$  and  $\leq 48$  hours,  $>48$  and  $\leq 72$  hour,  $>72$  hours), and overall (across over the course of approximately 72-hours of continuous infusion).

Other safety measures will include AEs, hypoglycemia, vital signs and weight, treatment exposure, laboratory measures, and antibodies to insulin lispro. Analyses will be performed on data collected over the 6-week treatment period for each treatment group.

Events that are newly reported after the first dose of IP or reported to worsen in severity from baseline will be considered TEAEs. The Medical Dictionary for Regulatory Activities (MedDRA) lowest level term (LLT) will be used in the treatment-emergent assessment. The maximum severity for each LLT during the baseline period will be used as baseline severity.

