Table ITSI.4.1.	Objectives and Endpoints.....	7
Table ITSI.6.1.	Patient Populations	13
Table ITSI.6.2.	Baseline and Post-Baseline Definitions and Patient Population by Study Period and Type of Analysis.....	15
Table ITSI.6.3.	Description of Important Protocol Deviations	21
Table ITSI.6.4.	Source Data for Infusion Set Changes	27
Table ITSI.6.5.	Adverse Event Analysis Periods	30
Table ITSI.6.6.	Summary of Analyses for Endpoints Related to Hypoglycemia.....	31
Table ITSI.6.7.	Categorical Criteria for Abnormal Treatment-Emergent Blood Pressure and Pulse Measurement, and Categorical Criteria for Weight Changes for Adults	35
Table ITSI.6.8.	Outcome Measures of CGM DATA.....	37

Table of Contents

Figure		Page
Figure ITSI.5.1.	Illustration of study design for Clinical Protocol I8B-MC-ITSI.....	10
Figure ITSI.5.2.	Flow chart for reporting infusion set changes.	11

3. Revision History

Statistical Analysis Plan (SAP) Version 1 was approved prior to the first patient visit. Version 1 is based on the Protocol I8B-MC-ITSI approved on 23 October 2017 and amended on Jan 12, 2018.

SAP Version 2 was approved on 26 April 2018. The main changes from Version 1 are listed below:

- adding analysis details (for example, analysis of time until infusion set changes) and rules (for example, to define unique hypoglycemia events).
- deleting the following analyses:
 - hypoglycemia summaries for postmeal all documented and documented unspecified hypoglycemia because the information of time relative to meal is missing for documented unspecified hypoglycemia events

This SAP is the third version approved prior to the first unblinding. The main changes from Version 2 are listed below:

- modifying the baseline definition for treatment-emergent adverse event (TEAE) analyses for the two 6-week randomized treatment periods: use observations prior to first dose of randomized investigational product (IP) (or Visit 3 date if the dose date is missing) but after the first dose of open-label lispro in the lead-in period.
- adding treatment-emergent potential hepatic disorder analyses.
- adjusting the hypoglycemia rate analysis methods to Wilcoxon signed-rank test only and removing the basal rate from hypoglycemia incidence analysis model, to address the model convergence issue due to the relatively small sample size of the study.
- adding more details as to how to identify a non-meal related correction bolus in electronic clinical outcomes assessment (eCOA) captured data.

4. Study Objectives

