
Table ITSI.4.1 shows the objectives and endpoints of the study.

Table ITSI.4.1. Objectives and Endpoints

Objectives	Endpoints
Primary Objective	
1. To compare LY900014 and insulin lispro with respect to the rate of infusion set failures that lead to premature infusion set changes, due to a pump occlusion alarm OR due to unexplained hyperglycemia with blood glucose >250 mg/dL (13.9 mmol/L) that does not decrease within 1 hour following a correction bolus delivered via the pump	1. Rate (events/patient/30 days) of infusion set failures that lead to premature infusion set changes, due to a pump occlusion alarm OR due to unexplained hyperglycemia with blood glucose (SMBG) >250 mg/dL (13.9 mmol/L) that does not decrease within 1 hour following a correction bolus delivered via the pump, during the 6-week treatment period
Secondary Objectives	
2. To compare LY900014 and insulin lispro with respect to the incidence of infusion set failures that lead to premature infusion set changes, due to a pump occlusion alarm OR due to unexplained hyperglycemia with blood glucose >250 mg/dL (13.9 mmol/L) that does not decrease within 1 hour following a correction bolus delivered via the pump	2. Incidence (percent of patients with at least 1 event) of infusion set failures that lead to premature infusion set changes, due to a pump occlusion alarm OR due to unexplained hyperglycemia with blood glucose (SMBG) >250 mg/dL (13.9 mmol/L) that does not decrease within 1 hour following a correction bolus delivered via the pump, during the 6-week treatment period
3. To compare LY900014 and insulin lispro with respect to the rate and incidence of premature infusion set changes	3. Rate (events/patient/30 days) and incidence of premature infusion set changes by reason (infusion set kinked, came out, or leaking; empty pump reservoir; infusion site pain or redness; pump occlusion alarm; suspected infusion set occlusion; other) during the 6-week treatment period
4. To compare LY900014 and insulin lispro with respect to the time interval until infusion set change	4. Time interval until infusion set change during the 6-week treatment period
5. To compare LY900014 and insulin lispro with respect to total, basal, and bolus insulin dose	5. Bolus/total insulin dose ratio at the end of the 6-week treatment period

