Unless otherwise specified, a restricted maximum likelihood based, mixed-effect model repeated measures (MMRM) analysis will be used to analyze continuous longitudinal variables. All the longitudinal observations at each scheduled postbaseline visit during the 6-week treatment period for each treatment group will be included in the analysis. An unstructured covariance structure will be used to model the within-patient errors. Significance tests will be based on LS means and Type III tests. SAS PROC MIXED will be used to perform the analysis.

- MMRM-Model 1: for analysis of variables that are measured at multiple designated visits within each randomized treatment period (e.g., weight and vital signs), the model will include the fixed class effects of treatment, period, sequence, strata (region, historical use of SmartGuard/Threshold Suspend, HbA1c), week (relative to the start of each randomized treatment period), and week-by-treatment interaction, and the continuous, fixed covariate of baseline value. If the analysis fails to converge, the following covariance structures will be tested in order:

- Compound symmetry with heterogeneous variances
- Compound symmetry without heterogeneous variances
- MMRM-Model 2: for analysis of variables that are only measured once for each randomized treatment period (e.g., 1,5 AG), the model will include the fixed class effects of treatment, period, sequence, strata (region, historical use of SmartGuard/Threshold Suspend, HbA1c), and the continuous, fixed covariate of baseline value (Grizzle 1965). If this analysis fails to converge, a covariance structure of compound symmetry without heterogeneous variances will be used.

The Kenward-Roger approximation will be used to estimate denominator degrees of freedom. For either of the two models, if the model fails to converge for any covariance structure, strata may be deleted from the model.

For categorical measures (such as incidence of AEs), summary statistics will include sample size, frequency, and percentages. Prescott's test will be used for treatment comparisons, unless otherwise specified.

For laboratory values, both conventional (CN) and Systeme International (SI) units will be presented. Therefore, both % and mmol/mol will be presented for HbA1c and both mg/dL and mmol/L will be presented for glucose measurements.

Table ITSI.6.2. Baseline and Post-Baseline Definitions and Patient Population by Study Period and Type of Analysis

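### Does leaving the composite out of the SAP 6.11.2 test list leave secondary objective 2 without an analysis?

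*SAP*

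**What the plan says.** SAP Table ITSI.4.1 gives the endpoint for secondary objective 2 as "Incidence (percent of patients with at least 1 event) of infusion set failures that lead to premature infusion set changes", with both limbs of the primary definition (occlusion alarm, or hyperglycemia above 250 mg/dL that does not decrease within 1 hour of a pump correction bolus). Protocol 10.3.3.2 assigns Prescott's exact test to the same quantity: "The incidence (percent of patients with at least 1 event) of infusion set failures, as defined in the primary objective". The Protocol synopsis does likewise.

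SAP 6.11.1 defines the composite event and specifies a Wilcoxon signed-rank test of its rate. SAP 6.11.2 then lists four endpoints whose incidence and rate are to be tested by Prescott's and Wilcoxon's tests:

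- "suspected infusion set occlusions defined as unexplained hyperglycemia with blood glucose (SMBG) >250 mg/dL", with no decrease after a correction bolus, leading to a set change;
- "infusion set failures leading to premature infusion set changes due to unexplained hyperglycemia with blood glucose >250 mg/dL", under the rule of no fall greater than 50 mg/dL;
- "premature infusion set changes for any reason and for each individual reason";
- severe hypoglycemia.

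Just below, the same section plans the number of events and the number of patients with events for infusion set failures, for each treatment group, by catheter dwell time and overall.

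The section also plans a listing of premature changes due to unexplained hyperglycemia. One of its columns flags the >50 mg/dL endpoint, described in a parenthesis as one that "leads to premature infusion set changes, due to a pump occlusion alarm OR due to unexplained hyperglycemia".

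SAP 6.1 states the general rule for categorical measures, namely that Prescott's "test will be used for treatment comparisons, unless otherwise specified".

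**The concern.** SAP 6.11.2 is where a programmer would look for the secondary tests, and the composite incidence is the first-listed secondary objective. Finding a narrower event at the head of the list, one could produce a hyperglycemia-only table and an alarm-only table and never the combined one. The two separate incidences do not determine the combined incidence, because one patient may have both kinds of event, and the combined test can disagree with both component tests. The SAP's Revision History, introduced by "The main changes from Version 2 are listed below", records no decision to drop the combined test, so the gap looks unintended.

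The parenthesis in the listing raises a lesser worry. The >50 mg/dL endpoint appears with an alarm limb there and without one in the tested entry and in Protocol 10.3.3.2, so two people could code it differently.

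**Working it through.** **The plan's own figure.** SAP 5.2 states about 42 completers and 12% dropout: 42 / (1 − 0.12) = 47.7, rounded up to 48 randomized, as stated. Nothing in this point touches that number or the two-sided 0.05 level. The plan states no power.

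**What could be at stake if the combined table were never made.** If the component incidences are pA and pH, the composite lies between max(pA, pH) and min(1, pA + pH). Take 42 completers, 21 per sequence, with discordant patients split equally between sequences. The event counts are assumptions; the documents give none. Let each component occur in 8 patients on LY900014 only and 2 on lispro only.

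| Case | LY900014 | Lispro | Prescott two-sided p |
|---|---|---|---|
| Each component alone | 8/42 = 19.0% | 2/42 = 4.8% | 0.114 |
| Composite, same patients have both events | 8/42 = 19.0% | 2/42 = 4.8% | 0.114 |
| Composite, no patient has both | 16/42 = 38.1% | 4/42 = 9.5% | 0.013 |

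So the combined result does carry information that the components lack. The question is whether the plan leaves it underived or untested.

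**Is the composite derived?** Yes, by two routes.

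1. SAP 6.11.1 requires, for each patient in each period, the number of composite events while on pump and on study treatment. That number is the numerator of the primary rate. A patient counts toward incidence exactly when it is at least 1, so no new derivation is needed.
2. The dwell-time paragraph of SAP 6.11.2 asks for the overall number of patients with infusion set failures in each treatment group. The matching sentence in Protocol 10.3.3.2 ties those failures to the primary definition.

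Nobody has to reconstruct the composite from its components, so the 19.0% to 38.1% range above does not arise in practice.

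**Is the test specified?**

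| Place | Content |
|---|---|
| SAP Table ITSI.4.1 | Keeps composite incidence as secondary objective 2 |
| Protocol synopsis and 10.3.3.2 | Prescott's exact test for this incidence |
| SAP 6.1 | Prescott's test by default for categorical measures; nothing specifies otherwise here |
| SAP 6.1 | A departure from protocol methods is to be described and justified in the SAP or study report; the SAP describes none on this point |
| SAP 6.11.2, opening paragraph | Safety Population, data up to last dose in each period, off-pump and off-treatment data excluded |

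The endpoint, event definition, data rules and test are all fixed, and they agree.

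**The listing parenthesis.** The listing contains only premature changes due to unexplained hyperglycemia. Under Protocol 9.1.4.1.2 each premature change has one primary reason, so a change attributed to an alarm cannot be a row in it; alarm changes have a separate listing. Within these rows the flag has the same value with or without the alarm clause. The tested >50 mg/dL entry and Protocol 10.3.3.2 agree with each other, so the tested result has one definition.

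**The case for a change.** The best case for acting is that 6.11.2 is the operative section for secondary tests, that a general default is a weak substitute for naming the first secondary objective, and that one added line would cost almost nothing. It is true that the list omits the composite, that the p-values in the illustration are correct, and that the component tests cannot stand in for the combined one.

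The consequence does not follow. To miss the combined test, a programmer would have to overlook the objectives table in the same SAP, the explicit assignment in the protocol, the SAP default, and the planned patient counts in the same section. The illustration also compares two extremes, complete and zero overlap, with invented counts; Protocol 5.1 expects unexplained hyperglycemia to be uncommon. Crossing 0.05 would carry little weight in any case: SAP 5.2 says the trial is not designed or powered for superiority or non-inferiority, SAP 6.5 applies no multiplicity control to secondary endpoints, and no success rule depends on this p-value.

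The silence of the Revision History proves little, since it lists only main changes. The resemblance of the first entry to superseded endpoint wording is no firmer: the replaced definition in Protocol Appendix 8 used a different threshold (>300 mg/dL) and a required fall of >50 mg/dL.

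**Conclusion.** No change follows. The missing list entry is a gap that the rest of the documents already fill, and the alarm clause in the listing is a clerical slip without effect. Followed as written, the plan gives the same composite count by treatment and the same Prescott's exact test as it would with the entry restated. The differences in sample size, alpha, tested definitions and listed rows are all nil.

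This rests on two readings: that the protocol's method stands where the SAP describes no departure from it, and that the infusion set failures counted in SAP 6.11.2 are those defined in SAP 6.11.1, as the parallel sentence in the protocol says. Both are the natural reading, and nothing in either document points the other way.

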5.1. Summary of Study Design

Study I8B-MC-ITSI is a Phase 3, prospective, randomized, double-blind, outpatient, multinational, multicenter, 2-treatment group, crossover, active-controlled study conducted in patients with type 1 diabetes (T1DM) currently using CSII. In the 2 treatment groups, LY900014 and insulin lispro, meal bolus doses will be delivered immediately prior to each meal (0 to 2 minutes) in a double-blind manner.

The study includes a 1-week screening period and a 2-week lead-in period followed by a 2-period (Period I and Period II) crossover and a 4-week post-treatment safety follow-up. Each period of the crossover will consist of 6 weeks of treatment with no washout between periods.

Figure ITSI.5.1 illustrates the study design.

[figure not shown]

Figure ITSI.5.1. Illustration of study design for Clinical Protocol I8B-MC-ITSI.

Patients who need to discontinue from study treatment will also be discontinued from the study. Please refer to Protocol Sections 8.1 and 8.2. In this document, discontinuation of IP refers to the last dose of IP in a study period (lead-in, Period I, or Period II).

The eCOA diary will be used by patients to document 4-point SMBGs (consists of fasting [pre-morning meal], pre-midday meal, pre-evening meal, and pre-bedtime), hypoglycemia, and all infusion set changes, including date and time of change, designation of routine or premature change, primary reason for premature change (infusion set kinked, came out, or leaking; empty

pump reservoir; infusion site pain or redness; pump occlusion alarm; suspected infusion set occlusion; other) as depicted in Protocol 9.1.4.1. Additional data on infusion site complications will be collected by investigators.

Patients will enter all non-meal-related correction boluses into the eCOA diary. In the case of suspected infusion set occlusion, patients will choose or enter a new correction bolus from the eCOA diary that corresponds to the time of the suspected occlusion. They will then indicate if the correction bolus was given via pump or via syringe. If more than one correction bolus is given, patients should choose the first non-meal related correction bolus. This information is also critical in order to evaluate the primary objective of the study.

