6.11. Safety Analyses

6.11.1. Primary Outcome and Methodology

The primary objective of this study is to compare LY900014 and insulin lispro with respect to the rate (events/patient/30 days) of infusion set failures that lead to premature infusion set changes, due to a pump occlusion alarm OR due to unexplained hyperglycemia with blood glucose (SMBG) >250 mg/dL (13.9 mmol/L) that does not decrease within 1 hour following a correction bolus delivered via the pump, during the 6-week treatment period.

To be considered as the primary endpoint, an infusion set failure must result in a premature infusion set change due to:

1. pump occlusion alarm(s), OR
2. unexplained hyperglycemia that meets the following conditions:
 - Associated with a non-meal-related correction bolus delivered via the pump at least 1 hour before the infusion set change
 - Most recent self-monitored blood glucose (SMBG) within 1 hour before the correction bolus >250 mg/dL (13.9 mmol/L)
 - At least 1 SMBG obtained following the correction bolus prior to the infusion set change
 - Within 1 hour (+10 minutes) following the correction bolus, the most recent SMBG prior to the infusion set change does not indicate a decrease in blood glucose

If more than 1 non-meal-related correction bolus is given for an unexplained hyperglycemia, only the first correction bolus time will be used to determine the 1 hour (+10 minutes) timeframe following the correction bolus as described in Section 9.1.4.1.2 of the protocol.

For each treatment period (lead-in, Period I and Period II), the infusion set failure rate (events/patient/30 days) will be calculated for each patient as the total number of events while the patient is on pump and on study treatment divided by the days of exposure [last dose date and time – first dose date and time – duration of pump or treatment interruption] times 30.

The analyses of the primary objective will be conducted on the Safety Population including data collected prior to permanent discontinuation of investigational product (i.e., last dose) in each randomized treatment period (Period I and Period II) and excluding data (if any) that are collected while patients temporarily are off pump or off IP. Treatment group comparisons will be performed using Wilcoxon signed-rank test at the full significance level of 0.05, with patients who are dosed in both treatment periods.

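### Failures by catheter dwell time are planned as raw counts with no sets or set-hours at risk, so they cannot be read as a profile over wear time

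*SAP*

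**What the plan says.** SAP 6.11.2 plans, for infusion set failures and premature set changes, that "the number of events and the number of patients with events will be derived for each treatment group by infusion set catheter dwell time". The bins are up to 24 hours, over 24 to 48, over 48 to 72, and an open last bin: ">72 hours), and overall (across over the course of approximately 72-hours of continuous infusion". Protocol 10.3.3.2 has the same plan: "the number of events and the number of patients with events will be derived for each treatment group". Neither document gives a number of sets in place, hours at risk, a rate per bin or a time-to-failure curve.

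The related outputs do not fill the gap:

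- The failure rate in SAP 6.11.1 is "divided by the days of exposure", but that denominator covers the whole period and is not split by dwell time.
- The time interval until set change (SAP 6.11.2) is one average per patient and period.
- The set-change listings specified in SAP 6.11.2 cover premature changes only. Sets that ended in a routine change are not listed, so the number at risk cannot be rebuilt from them.

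The data for a denominator exist. The SAP states that date and time "of all infusion set changes will be collected in the database by either eCRF or eCOA".

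**The concern.** A count by dwell time mixes two things: how likely a set is to fail at that age, and how many sets reach that age. Each premature change removes a set from the later bins and starts a new one in the first bin. The schedule then removes most of the rest, since "The protocol requires that patients change infusion set every 72 ± 4 hours". The count therefore tends to fall along the row whatever the hazard does.

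A reader of such a table could conclude that failures become less frequent as the catheter ages, or could miss a modest real rise late in wear. If the two insulins differ in how often sets are changed early, the same mechanism raises the early counts and lowers the late counts on the treatment with more changes, even at equal failure hazard.

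**Working it through.** **The plan's own figure.** The documents state no figure for this table. The only sample-size figure is 48 randomized for 42 completers with 12% dropout: 42 / 0.88 = 47.7, rounded up to 48. It reproduces and is not affected.

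**Inputs.**

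- 42 patients (SAP 5.2), each with 42 days per treatment: "Each period of the crossover will consist of 6 weeks of treatment with no washout between periods". That is 42 × 42 = 1,764 set-days per treatment.
- Routine change at 68 to 76 hours. A uniform spread within that window is assumed.
- Failure rates of 0.44 and 2 per patient per 30 days (assumed). The current plan gives no rate. These two come from the deleted power paragraph in the Amendment (a) summary and serve only as a range.
- Other premature changes at 0, 1 and 3 per patient per 30 days (assumed).

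**Method.** Successive sets were simulated for each patient. Each set ended at the first of failure, other premature change, routine change or end of period. As a check, expected failures in a bin equal the hazard per set-day times the set-days in that bin.

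**Step 1: a constant hazard.** With 0.44 failures and 1 other premature change per 30 days:

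| | ≤24 h | >24–48 h | >48–72 h | >72 h |
|---|---|---|---|---|
| Sets in place at bin start | 653 | 608 | 567 | 263 |
| Set-days at risk | 629.8 | 587.2 | 525.2 | 21.8 |
| Failures | 9.23 | 8.61 | 7.71 | 0.29 |
| Failures per 100 sets | 1.41 | 1.42 | 1.36 | 0.11 |
| Failures per 100 set-days | 1.46 | 1.47 | 1.47 | 1.31 |

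The set-days add to 1,764. The hazard is 0.44 / 30 = 0.01467 per set-day. Multiplied by the set-days, it gives 9.24, 8.61, 7.70 and 0.32 failures, which agrees with the simulation. The gap in the last bin (0.29 against 0.32) is simulation error on less than one event.

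The count falls by 1 − 7.71/9.23 = 16% over the first three bins, while the rate per set-day is flat. Dividing by sets alone does not repair the last bin (0.11 against about 1.4), because each set spends so little time there. Hours are needed.

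**Step 2: the range.**

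| Failures / other changes per 30 days | Count ≤24 h | Count >48–72 h | Apparent fall |
|---|---|---|---|
| 0.44 / 0 | 8.90 | 8.01 | 10% |
| 0.44 / 1 | 9.23 | 7.71 | 16% |
| 0.44 / 3 | 9.82 | 7.23 | 26% |
| 2 / 0 | 42.84 | 34.63 | 19% |
| 2 / 1 | 44.25 | 33.31 | 25% |
| 2 / 3 | 46.90 | 30.95 | 34% |

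The >72 h count is about 2.5% (0.25/9.82) to 3.4% (0.30/8.90) of the first bin. Exposure there is about 18 to 23 set-days, against 606 to 703 in the first bin.

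**Step 3: the two treatments side by side.** Base failure rate 0.44; ratio of counts, one treatment to the other:

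- Failure hazard 2 to 4.55 times higher in the first 48 hours and equal afterwards: the >48–72 h count ratio is 0.99 to 0.95, where the true hazard ratio is 1. Per set-day it is 0.99 to 1.00.
- Equal failure hazard, other premature changes 2 to 4 times more frequent from a base of 1 per 30 days: 1.03 to 1.09 (≤24 h) and 0.96 to 0.90 (>48–72 h).
- The same from a base of 3 per 30 days: 1.09 to 1.27 and 0.89 to 0.70. Set-days move by the same factor (for example 1.275 and 0.704 at 4-fold), so division brings both ratios back to about 1.

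**The case against.** The strongest reply is that this is an untested descriptive table and that the treatment question is answered elsewhere. Much of that stands.

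- A reader might infer that a planned treatment comparison within bins is biased. The documents do not support this. SAP 6.11.2 assigns Prescott's exact test and the Wilcoxon signed-rank test to overall incidence and rate, and plans no test, model or decision rule within bins.
- A reader might infer that raw counts hide late failures on LY900014. The size does not support that. With about 8 failures expected in a bin, a 10% shift is under one event, against Poisson variation of about √8 ≈ 3. The crossover also gives each patient about six weeks on both treatments, and overall premature changes, changes by reason and time until change are all analysed. For premature changes as a class, unequal early change is itself a difference in hazard, so the equal-hazard argument applies only to failures.
- A reader might take the >72 h bin to cover at most 4 hours. That holds only under full adherence. SAP 6.11.2 keeps intervals up to 168 hours in the interval analysis, and SAP Table ITSI.6.3 flags a deviation only when at least 75% of routine changes miss the window. Exposure in the open bin is therefore unknown, which is itself a reason to report it.
- Neither document states an aim for this table. Protocol 10.3.3.3 states a 72-hour aim only for CGM glucose control.

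None of this answers the point about reading across bins. The counts are laid out by wear time, and no planned output supplies the denominator.

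**Conclusion.** The point holds for the profile over wear time. As planned, a flat failure hazard would be displayed as falling by about 10% to 34% from ≤24 h to >48–72 h. It would almost vanish after 72 hours if patients keep to 72 ± 4 hours. These sizes rest on assumed failure and premature-change rates. At the lower failure rate the fall is only about 1 to 3 events (8.90 to 8.01, and 9.82 to 7.23), so the fault is one of interpretation more than of large numbers.

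For the display by treatment, the counts can be distorted. The bias is 1% to 5% in the >48–72 h bin when only early failure rates differ. It reaches 10% to 30% only with a 2- to 4-fold difference in other premature changes from 3 per 30 days, or a 4-fold difference from 1 per 30 days. Whether such changes differ is a secondary question of the study, so equality cannot be presumed. The primary analysis and the sample size are not affected. This is a worthwhile improvement, not a flaw in the main conclusions.

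**What to change.** In SAP 6.11.2, keep the planned counts and add, per bin and treatment:

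- the number of sets in place at the start of the bin;
- set-hours at risk while on pump and on IP;
- failures per 1,000 set-hours (in Step 1, 0.01467 / 24 × 1,000 = 0.61).

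State that other set changes and the end-of-period office change end time at risk, and whether they are treated as censoring or as competing events. Do not cut off at 76 hours; report the >72 h bin with its actual exposure. If intervals are given around the rates, allow for clustering of sets within patient.

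Say how the exclusions in SAP 6.11.2 enter the denominator, so that numerator and denominator match. They are redundant entries within 1 hour, "any patient-reported routine infusion set change that occurred within 24 hours of a previous infusion set change", and intervals over 168 hours. For example, dropping a routine change could either remove a set or merge two sets into one with a longer dwell time, and the rule should say which.

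The cost is a small amount of derivation and a few table columns. No new data, visits or patients are needed.
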